9.2.3 Safety Analysis Plan

The safety analysis will comprise descriptive statistics, tabulations and listings of all treatment emergent adverse events (TEAEs), safety laboratory results, viral markers, vital signs, physical examination findings, and any other relevant safety information as detailed in Section 7.3.

9.2.3.1 Adverse Events

All reported AEs will be coded according to Medical Dictionary for Regulatory Activities (MedDRA).

An AE is defined as treatment-emergent, if first onset or worsening is after start of the first IMP administration. Only TEAEs are accounted for in the analysis.

A TEAE will be considered to be temporally associated with the infusion (or ‘infusional’) if it starts during or within 72 hours of the end of the infusion.

Incidences of TEAEs will be given as numbers and percentages of patients and infusions with:

- Any TEAE
- Any serious TEAE
- Any TEAE probably or possibly related to the trial drug
- Any severe TEAE
- Number of infusional TEAEs
- Number and percentage of infusions temporally associated with one or more TEAE
- Any withdrawal due to TEAE
- Any significant TEAE (see Section 7.3.1.1)
- Any TEAE by MedDRA Preferred Term (PT)
- Any TEAE by MedDRA System Organ Class (SOC)

Summary tables for TEAEs will be given by System Organ Class (SOC) and Preferred Term (PT). Additionally, TEAEs will be summarized by severity and relationship to study treatment.

All TEAEs for each patient, including multiple occurrences of the same event, will be listed in full detail, including reported term, MedDRA PT and SOC, onset, duration, time to the AE occurrence from last dose, causality, dosage, severity, seriousness and actions taken.

Narratives will be prepared describing each death, other SAEs, and other significant TEAEs that are judged to be of special interest because of clinical importance.

9.2.3.2 Laboratory Safety Tests

The safety laboratory data (Clinical chemistry, hematology, and urinalysis) will be converted to standard units during the data management process. The laboratory data will be listed with suitable flags indicating abnormal values (L=Lower than reference range, H=Higher than reference range) and clinical significance as judged by the investigator whenever available.

Summary statistics for the laboratory values as well as their changes from baseline at each time point will be tabulated.

9.2.3.3 Viral Safety tests

All viral marker results will be listed, and shift tables will be used to identify any possible seroconversion during the course of the study.

9.2.3.4 Vital Signs

Vital signs parameters will be summarized by visit, using the standard set of summary statistics for both, absolute values and changes from baseline.

9.2.3.5 Physical Examination

Shift tables will be used to identify changes in the assessments between visits. New or worsened symptoms/findings will be listed individually.

9.2.3.6 Other Relevant Safety Information

All additional safety information collected in the study will be listed and reviewed. If judged to be of relevance, narratives will be prepared to describe any such results in full detail.

9.2.4 Handling of Missing Data

In general, missing data will not be imputed, and all data derivations will be based on observed values only. Only in case of missing body weight, the last available weight measurement will be used for calculating the dose per kg bodyweight (last observation carried forward).

If missing values occur in the confirmatory analysis of the primary endpoint in the FAS, they will be imputed by worst observed values, i.e. the patient concerned will be analyzed as non-responder.

9.3 Randomization / Stratification / Code Release

All patients still qualified to participate in the study at Visit 2 will be randomized to one of the three treatment arms by an electronic IWRS tool. The randomization will apply a randomization ratio of 1:2:1 with respect to the dosage groups of 0.5, 1.0, and 2.0 g/kg of NewGam by means of a stratified block design, using the treatment before enrollment (immunoglobulin or corticosteroids treatment) as strata and a fixed block size. This will ensure the desired overall randomization ratio and avoid random differences between the dosage groups with respect to the CIDP treatment used prior to enrollment into the ProCID study.

The randomization scheme will only be available to the statisticians responsible for creating it, and the programmer implementing the scheme into the IWRS system. No information on treatment assignment will be communicated to the sponsor or any CRO personnel responsible for the conduct of the study or the analysis of data.

The result of randomization, i.e. the treatment group assignment of individual patients will only be reported to the hospital pharmacist or designee by a dedicated email that no other trial personnel will have access to.

Blinding will not be broken while the study is ongoing, unless in case of medical emergencies as described in Section 5.8. Only after completion of all procedures related to data cleaning, the medical review of the data, the finalization of the statistical analysis plan, the agreement on the final patient disposition, and the formal database lock the blind will be broken and the individual treatment assignment will be added to the clinical database for analysis.

9.4 Interim Analysis

No interim analysis is planned.

10 ETHICAL / REGULATORY, LEGAL AND ADMINISTRATIVE ASPECTS

10.1 Ethical / Regulatory Framework

This study will be conducted in accordance with the ethical principles laid down in the Declaration of Helsinki. The study protocol and any subsequent amendment(s) will be submitted to an Independent Ethics Committee (IEC) / Institutional Review Board (IRB) and to the Regulatory Authority. The study will be conducted in compliance with the protocol, ICH-GCP E6 regulations and applicable regulatory requirements.

The regulatory application or submission for regulatory approval will be made by the Sponsor or designated third party (e.g. CRO) as required by national law and in accordance with FDA/Regulatory Authority regulations.

10.2 Approval of Study Documents

The study protocol, a sample of the patient information and informed consent form, any other materials provided to the patients, and further requested information will be submitted by the Sponsor or the Investigator to the appropriate IEC/IRB and the Regulatory Authority. The study approval letter must be available before any patient is exposed to a study-related procedure.

The Sponsor, the Investigator and any third party (e.g., CRO) involved in obtaining approval, must inform each other in writing that all ethical and legal requirements have been met before the first patient is enrolled in the study.

10.3 Patient Information Sheet and Informed Consent Form

The Investigator will obtain freely given written consent from each patient after an appropriate explanation of the aims, methods, anticipated benefits, potential hazards and any other aspect of the study which is relevant to the patient's decision to participate. An English master version of the patient information sheet and the informed consent form will be translated into local languages. The informed consent form must be signed, with name and date and time noted by the patient, before the patient is exposed to any study-related procedure, including screening tests for eligibility.

The Investigator will explain that the patients are completely free to refuse to enter the study or to withdraw from it at any time, without any consequences for their further care and without the need to justify. The Investigator will complete the informed consent section of the CRF for each patient enrolled.

Each patient will be informed that his/her medical (source) records may be reviewed by the study monitor, a quality assurance auditor or a health authority inspector, in accordance with applicable regulations, and that these persons are bound by confidentiality obligations.

10.4 Protocol Amendments

Any prospective change to the protocol will be agreed between the Investigator (Co-ordinating Investigator in multicenter studies) and the Sponsor prior to its implementation. Any such amendments will be submitted to the IEC/IRB(s) and/or competent authority responsible as required by applicable regulations. IEC/IRB(s) approval will at a minimum be requested for any change to this protocol which could affect the safety of the patients, the objective/design of

the study, any increase in dosage or duration of exposure to the IMP, an increase in the number of patients treated, the addition of a new test or procedure, or the dropping of a test intended to monitor safety.

10.5 Confidentiality of Patients' Data

The Investigator will ensure that the patient's confidentiality is preserved. In eCRFs or any other documents submitted to the Sponsor, the patients will not be identified by their names, but by a unique patient number. Documents not for submission to the Sponsor, i.e., the confidential patient identification code list, original consent forms and source records will be maintained by the Investigator in strict confidence.

11 QUALITY CONTROL AND QUALITY ASSURANCE

11.1 Periodic Monitoring

The monitor will contact and visit the Investigator periodically to review all study-related source data/records, verify the adherence to the protocol and the completeness, correctness and accuracy of all eCRF entries compared to source data. The Investigator will co-operate with the monitor to ensure that any discrepancies identified are resolved.

For this study, the first monitoring visit shall take place shortly after the inclusion of the first patient. Thereafter, monitoring frequency will depend on study progress, but is expected to be every 10 to 12 weeks depending on the sites' performance and recruitment rate.

The monitor must be given direct access to source documents (original documents, data and records). Direct access includes permission to examine, analyze, verify and reproduce any records and reports that are important to the evaluation of the clinical study. Source data will be available for all data in the eCRFs, including all laboratory results.

11.2 Audit and Inspection

The Investigator will make all study-related source data and records available to a qualified quality assurance auditor mandated by the Sponsor, or to IEC/IRB/regulatory inspectors, after reasonable notice. The main purposes of an audit or inspection are to confirm that the rights and welfare of the patients have been adequately protected, and that all data relevant for the assessment of safety and effectiveness of the IMP have been reported to the Sponsor.

12 REPORTING AND PUBLICATION

12.1 Clinical Study Report

A clinical study report (CSR; in accordance with relevant guidelines and Sponsor's SOPs) will be prepared by the Sponsor or designee after the completion of the study. The Co-ordinating Investigator will approve the final study report after review.

12.2 Publication Policy

The results of this study may be published or presented at scientific meetings. If this is envisaged by an Investigator, the Investigator agrees to inform the Sponsor and to submit all manuscripts or abstracts to the Sponsor prior to submission to an editorial board or scientific review committee. This will allow the Sponsor to protect proprietary information and to provide comments based on information that may not yet be available to the Investigator.

In accordance with standard editorial and ethical practice, the Sponsor will support publication of multicenter studies only in their entirety and not as individual center data. Authorship will be determined by mutual agreement.

13 LIABILITIES AND INSURANCE

In order to cover any potential damage or injury occurring to a patient in association with the IMP or the participation in the study, the Sponsor will contract insurance in accordance with local regulations.

The Investigator is responsible for dispensing the IMP according to this protocol, and for its secure storage and safe handling throughout the study.

15 APPENDICES

Appendix 1: Inflammatory Rasch-built overall disability sum score (I-RODS)

Appendix 2: Modified Fatigue Severity Scale (FSS)

Appendix 3: SF-36 Health Survey

octa pharma

Statistical Analysis Plan

Study ID NGAM-08

[figure not shown]
Study title Prospective, Double-Blind, Randomized, Multicenter Phase III Study Evaluating Efficacy and Safety of Three Different Dosages of Newgam in Patients With Chronic Inflammatory Demyelinating Poly(Radiculo)Neuropathy (ProCID study)

Study phase III

Document author
Document version
Final 03
Supersedes
2.0
Effective date
06-Jun-2019
Doc ID
2969

Protocol version this SAP is based upon Version 04 (dated 08-JUN-2018)

Approved by

Document History

Version	Date	Author	Description
Final v1	17-Dec-2015		New document
Final v2	16-Dec-2016		Incorporation of protocol changes based on FDA feedback to protocol version 1. Specifications with respect to the randomization strata.
Final v3	06-Jun-2019		Incorporation of protocol changes (v4)
			Details added on planned statistical analyses: Primary endpoint: Logistic regression
			Secondary endpoints: ANCOVA for changes from baseline in I-RODS total score; grip strength; MRC sums score; FSS total score; NCS measurements; QoL scores; ANCOVA models will be used for LSMEANS calculation (+95% CI) in various subgroups
			Logistic regression for responses based on I-RODS; based on grip strength; based on MRC sum score
			For INCAT disability total score and PI-NRS 95% confidence intervals for the median are added.
			Kaplan-Meier analysis for time-to response variables
			Deterioration after Wash-out/during dose evaluation added

Abbreviations

AE	Adverse Event
ВМІ	Body Mass Index
CI	Confidence Interval
CIDP	Chronic Inflammatory Demyelinating Poly(Radiculo)Neuropathy
CSR	Clinical Study Report
DB	Database
ECG	Electrocardiogram
(e)CRF	(Electronic) Case Report Form
EFNS	European Federation of Neurological Societies
FAS	Full Analysis Set
FDA	Food and Drug Administration

ITT	Intention-To-Treat			
I-RODS	Inflammatory Rasch-built Overall Disability Scale			
IWRS	Interactive Web Response System			
MADSAM	Acquired Demyelinating Sensory And Motor Neuropathy			
MCS Mental Composite Score MedDRA Medical Dictionary for Regulatory Activities MRC Medical Research Council				
		NAT		
		NCS		
PCS Physical Composite Score				
PNS	Peripheral Nerve Society			

Statistical Analysis Plan for NGAM-08

FSS	Fatigue Severity Scale	
GCP	Good Clinical Practice	
HBV	Hepatitis B Virus	
HCV	Hepatitis C Virus	
HIV	Human Immunodeficiency Virus	
ICH	International Conference on Harmonisation	
IgG	Immunoglobulin G	
IGIV	Intravenous Immunoglobulin	

The structure and content of this SAP provides sufficient detail to meet the requirements identified by the FDA and International Conference on Harmonization (ICH) of Technical Requirements for Registration of Pharmaceuticals for Human Use: Guidance on Statistical Principles in Clinical Trials¹.

The following documents were reviewed in preparation of this SAP:

Clinical Study Protocol NGAM-08, Version 04

The reader of this SAP is encouraged to also read the clinical protocol for details on the planned conduct of this study. Operational aspects related to collection and timing of planned clinical assessments are not repeated in this SAP unless relevant to the planned analyses.

¹ International Conference on Harmonization. (1998). Guidance on Statistical Principles. ICH Topic E9 (Statistical Principles for Clinical Trials) (p. 37). London: International Conference on Harmonization.

2. Purpose

This SAP outlines all statistical analyses to be performed on data collected in study NGAM-08, and the resulting output that will be compiled to support the completion of the Clinical Study Report (CSR).

The planned analyses identified in this SAP will be included in regulatory submissions and/or future manuscripts. Exploratory analyses not necessarily identified in this SAP may be performed to support the clinical development program. Any post-hoc or unplanned analyses performed that are not identified in this SAP will be clearly identified in the respective CSR.

The statistical output provided to the medical writer of the CSR will closely follow the ICH guideline for industry on topic E3 (Structure and Content of Clinical Study Reports²) to facilitate the subsequent compilation of the CSR.

This statistical output will consist of tables, figures and listings, including

- Tables, figures and listings used or referenced in, or appended to the CSR as detailed in the remainder of this SAP (section 14 of the CSR)
 - Demographic data summary figures and tables
 - o Efficacy data summary figures and tables
 - Safety data summary figures and tables
- Listings provided as appendices to the CSR
 - Patient data listings (section 16.2 of the CSR)
 - Individual patient data listings (section 16.4 of the CSR) will be covered by inclusion of SAS datasets into the electronic submission to the authorities

A detailed list of all tables, figures and listings will be supplied in a separate document later when all feedback from authorities will be available.

_

² International Conference on Harmonization. (1996). Structure and Content of Clinical Study Reports. Structure and Content of Clinical Study Reports (Guideline for Industry) (S. 37). London: International Conference on Harmonization.

3. Study Objectives and Endpoints

3.1. Study Objectives

3.1.1. Primary Objective

• To provide confirmatory data on the effect of 1.0 g/kg NewGam every three weeks in patients with active CIDP based on the percentage of responders at Week 24, which should corroborate the existing evidence on efficacy of IGIV in CIDP as known from published literature.

3.1.2. Secondary Objectives

Secondary objectives are

- To assess the effect of 0.5 g/kg and 2.0 g/kg NewGam every three weeks in patients with active CIDP based on the percentage of responders at Week 24 compared to patients on 1.0 g/kg NewGam every three weeks
- To evaluate the safety of NewGam administration using various dosages in patients with CIDP
- To further evaluate the beneficial effect of three NewGam dosages in patients with CIDP by assessing different parameters/scores/scales

3.1.3. Exploratory Objectives

- To assess the primary and secondary objectives at 3 weeks after having provided rescue medication (if applicable)
- To further evaluate the beneficial effect of NewGam administration in patients with CIDP by additional assessments/scores including quality of life (QoL) measures

3.2. Study Endpoints (Target Variables)

3.2.1. Primary Target Variables

The primary (efficacy) endpoint is the proportion of responders in the 1.0 g/kg NewGam arm at Week 24.

A responder is defined as a patient with a decrease of at least 1 point on the adjusted INCAT disability score relative to baseline (week 0).

The adjusted INCAT (Inflammatory Neuropathy Cause and Treatment) disability score is a measure of activity limitation ranging from 0 (healthy) to 10 (unable to make any purposeful movements with arms and/or legs), and is frequently used as a primary endpoint in CIDP trials. Participants in study NGAM-08 are required to have an adjusted INCAT disability score between 2 and 9 at study entry.

The proportion of responders will be calculated as (# of responders) / (# of patients in analysis set) and presented together with the two-sided 95% Wilson-score confidence interval (CI).

In case the primary endpoint can't be evaluated for a patient due to missing data, this patient will be considered as non-responder in the intent-to-treat (ITT) analysis based on the full analysis set (FAS), whereas the same patient would be excluded from the per-protocol (PP) analysis.

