2.0 g (LD)	0.5g 1.0 g	0.5g 1.0 g	0.5g 1.0 g	0.5g 1.0 g	2.0 g (RT)	2.0 g (RT)	EOS
	2.0 g	2.0 g	2.0 g	2.0 g	EOS		

5. Patients deteriorating* after Week 15 and before Week 18

Week 0	Week 3	Week 6	Week 9	Week 12	Week 15	Week 18	Week 21	Week 24
2.0 g (LD)	0.5g 1.0 g	0.5g 1.0 g	0.5g 1.0 g	0.5g 1.0 g	0.5g 1.0 g	2.0 g (RT)	2.0 g (RT)	EOS
	2.0 g	2.0 g	2.0 g	2.0 g	2.0 g	EOS		

LD – Loading Dose, RT – Rescue Treatment, EOS – End-of-Study-Visit

* = adjusted INCAT disability score increase of at least 1 point

** = adjusted INCAT disability score remains unchanged

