4.1. Overall Study Design and Plan

Study NGAM-08 is designed as a prospective, double-blind, randomized, multicenter phase III study. The rationale for conducting this study is to confirm the published clinical results obtained with the 1.0 g/kg dosing in order to apply for market authorization of NewGam, and to evaluate different dosing options on both sides of the standard dose with respect to efficacy and safety.

Patients will be screened for eligibility and, if eligible, thereafter have to decrease their current medication (Immunoglobulins by 25% from infusion to infusion or corticosteroids as per the discretion of the Investigator at a rate to expect study entry within 6-12 weeks) for a maximum of 12 weeks (Wash-out Phase). Only patients who deteriorate in this phase, i.e. active patients who need treatment, will be randomized 1:2:1 between three different dosages of NewGam (0.5 g/kg, 1.0 g/kg or 2.0 g/kg NewGam), and enter the Dose-Evaluation Phase.

[figure not shown]
The two allowed types of treatment prior to enrollment – Immunoglobulins or Corticosteroids – will be considered as strata in a stratified block design randomization with fixed block size. An electronic IWRS tool will be used to realize the randomization ratio of 1:2:1 with respect to the dosage groups, in each of the strata independently.

During the 24-week Dose-evaluation Phase all patients will first receive an initial loading dose of 2.0 g/kg NewGam, followed by 7 maintenance dosages of 0.5 g/kg, 1.0 g/kg or 2.0 g/kg NewGam every 3 weeks as they were randomized to.

Patients not deteriorating in the 12-week Wash-out Phase will not be enrolled into the ProCID study as they are not having active CIDP.

In addition the following rescue treatment option will be available: two consecutive infusions of 2.0 g/kg NewGam at 3-week intervals for all patients in the 0.5 and 1.0 g/kg NewGam arms who are either stable at Week 6 or deteriorate after Week 3 and before Week 18. Patients in the 2.0 g/kg NewGam arm will drop-out if they are stable at Week 6 or deteriorating after Week 3 and before Week 21.

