6.2. Premature Termination of the Study

If early termination of the study becomes necessary, the sponsor and the investigator will ensure that adequate consideration is given to the protection of the patients' interests. Premature termination will be notified in accordance with applicable regulatory requirements. Early termination might concern the study as a whole or individual centers. In any case the blind will be maintained until all database locking procedures are completed and the database has been locked; this includes finalization of the statistical analysis plan, which will be adapted to cover any issues arising from the premature termination.

7. Analysis Populations

The following populations will be considered for the statistical analysis:

The **safety set (SAF)** will include all randomized patients who received at least part of one infusion of IMP.

The **full analysis set (FAS)** is defined according to the intention-to-treat principle, and will include all patients of the SAF for whom any data was collected post infusion of IMP. Every treated subject will be considered in the analysis according to his randomized treatment/dose assignment.

The **per-protocol set (PPS)** – being a subset of the FAS — will exclude patients with significant protocol deviations, which may have an impact on the evaluation of the primary study outcome parameter(s). This is the set of patients who participated in the study as intended and for whom the primary efficacy endpoint can be evaluated as planned.

All protocol deviations documented during the conduct of the study or identified at the data review process prior to DB lock will be reviewed and classified as minor or major and with respect to its effect on the planned analysis. Only major protocol deviations with the potential to significantly affect the study results or to invalidate the interpretation of the data obtained will lead to exclusion of patients from the PP set. This classification of protocol deviations is the joint responsibility of the clinical study manager, the study statistician, and Octapharma's responsible medical expert, and will be performed and documented before the database is locked and the statistical analyses are performed.

The analysis of safety will be based on the safety set.

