The evaluation of primary objective(s) will be performed for the FAS (intention-to-treat analysis) and for the PPS (per-protocol analysis). The ITT analysis is considered to be the most relevant, and will be presented first in the statistical report.

The evaluation of secondary objectives will be performed for the FAS, and in addition for the PPS in case the two populations differ by more than 5%.

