8.2. Withdrawals

Patients who withdraw from the study prematurely will be considered in all data presentations for which they contribute data; in particular patients who fail to perform an INCAT evaluation at week 24 will be considered to be non-responders in the analysis of the primary endpoint in the FAS.

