8.4. Derived and Computed Variables

The following derived and computed variables have been initially identified as important for the analysis of the primary and secondary target variables. It is expected that additional variables will be required. The SAP will not be amended for additional variables that are not related to the primary target or key secondary target variables. Any additional derived or computed variables will be identified and documented in the SAS programs that create the analysis files. If the SAP is not amended, further derivations related to primary and secondary target variables will be described in the CSR.

• Body Mass Index: BMI = (Body weight) / Height² [Unit: kg/m²]

• Response based on the adjusted INCAT disability score:

Yes, if [Score at week 24] ≤ [Score at Week 0] - 1 and patient did not receive rescue treatment; No otherwise (including patients discontinued before week 24 and patients receiving rescue treatment)

The same definition will be applied to other visits than week 24 to allow for an analysis of the time to first response. Time to first response will be censored at start date of rescue medication if a patient received rescue medication and did not show a response before. In case a patient did not show any response until termination visit and did not receive rescue medication, time to first response will be censored at termination visit.

Worsening with respect to INCAT disability score:

Worsening occurs if a patient score increases to at least 1 point above the Week 0 value.

• Response based on grip strength (Martin Vigorimeter):

Evaluate both hands. Yes, if [Strength at Week 24] \geq [Strength at Week 0] + 8kPa in the dominant or the non-dominant hand and patient did not receive rescue treatment; No otherwise (including patients discontinued before week 24 and patients receiving rescue treatment).

Response/Worsening based on the I-RODS score:

The individual Minimally Clinically Important Difference (MCID)-related SE (MCID-SE) score is derived for each visit and patient individually, and categorized as follows:

MCID-SE ≥ 1.96	clinically important improvement
0 < MCID-SE < 1.96	clinically unimportant improvement
MCID-SE = 0	no change
-1.96 < MCID-SE < 0	clinically unimportant deterioration
MCID-SE ≤ -1.96	clinically important deterioration

The individual MCID-SE values are computed through the Rasch person location values (logits) **R** associated with the I-RODS Summed Raw Scores as follows:

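### The SAP has two unreconciled rules for patients without a Week 24 score; applied literally, section 3.2.1 would remove protocol-adherent treatment failures from the per-protocol set

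*SAP*

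**What the plan says.** Four statements in the SAP bear on a patient who has no Week 24 adjusted INCAT score.

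- Section 3.2.1 makes such a patient a non-responder in the FAS, "whereas the same patient would be excluded from the per-protocol (PP) analysis".
- Section 7 describes the PPS as patients who took part as intended and "for whom the primary efficacy endpoint can be evaluated as planned". It also limits PPS exclusion to major deviations.
- Section 8.2 says that patients without a Week 24 INCAT evaluation "will be considered to be non-responders in the analysis of the primary endpoint in the FAS". It is silent on the PPS.
- Section 8.4, which derives the response variable, assigns "No otherwise (including patients discontinued before week 24 and patients receiving rescue treatment". It does not restrict this to one analysis set.

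The dosing rules decide who reaches Week 24. Under SAP 4.1, patients in the 2.0 g/kg arm "will drop-out if they are stable at Week 6 or deteriorating after Week 3 and before Week 21". Under Protocol 5.5 and 6.1.4, patients in the 0.5 and 1.0 g/kg arms who meet the rescue conditions receive two rescue infusions and have their final visit three weeks after the second. That visit falls at Week 12, 15, 18, 21 or 24. Protocol 5.7 puts the final visit at Week 21 for deterioration after Week 18, and at Week 24 for deterioration after Week 21.

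SAP 10.1 uses the PPS to judge the robustness of the primary result. Section 7 adds secondary analyses "in addition for the PPS in case the two populations differ by more than 5" percent.

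**The concern.** A per-protocol set should remove patients whose data do not reflect the planned treatment. Here a patient can follow every instruction, fail to respond, be taken off the schedule by the protocol's own rules, and so have no Week 24 score. If that absence counts as missing data under 3.2.1, the PPS selects on the outcome it is meant to check. The per-protocol response rate then rises whatever the drug does, and agreement between FAS and PPS says nothing about robustness. The dose comparison is a secondary objective and would be affected too if it were repeated in this set.

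**Working it through.** **Who lacks a Week 24 score under the rules.**

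- Stable at Week 6: final visit at Week 6 (2.0 g/kg) or Week 12 after rescue (0.5 and 1.0 g/kg). No Week 24 score in any arm.
- Deteriorating after Week 3 and before Week 15: final visit before Week 24 in every arm.
- "Patients deteriorating* after Week 15 and before Week 18" (schedule 5 in Protocol 5.5): final visit at Week 24 for 0.5 and 1.0 g/kg, but at Week 18 for 2.0 g/kg.
- Deteriorating between Weeks 18 and 21: final visit at Week 21.
- Deteriorating after Week 21: Week 24 visit kept.

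So failure is a main cause of a missing score in all arms, but not the only one (consent withdrawal and adverse events also produce it), and some failures keep a Week 24 visit.

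**The plan's own figure.** Inputs from Protocol 9.1: threshold 0.42, assumed rate 0.60, at least 80% power, 62 evaluable patients, 70 enrolled in the 1.0 g/kg arm. With p = x/n and z = 1.96, the Wilson lower limit is

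(p + z²/2n − z·√(p(1−p)/n + z²/4n²)) / (1 + z²/n).

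At n = 62 the smallest passing count is 34, with exact power 83.1%. At n = 61 it is also 34, with power 79.2%. From 62 to 71, the largest n checked, power stays at or above 80%. The stated 62 reproduces and is not in dispute.

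**Effect of literal 3.2.1 at a true 60%.** With N = 70 there are 42 responders and 28 non-responders. If a share f of the non-responders is removed, the per-protocol rate is 42 / (42 + 28(1 − f)).

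| f (assumed) | Removed | PPS n | PP rate | Wilson 95% CI |
|---|---|---|---|---|
| 0 | 0 | 70 | 60.0% | 48.3 to 70.7% |
| 25% | 7 | 63 | 66.7% | 54.4 to 77.1% |
| 50% | 14 | 56 | 75.0% | 62.3 to 84.5% |
| 75% | 21 | 49 | 85.7% | 73.3 to 92.9% |
| 100% | 28 | 42 | 100% | 91.6 to 100% |

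Under 8.4 nobody is removed for these reasons, and the first row applies to both FAS and PPS.

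**Effect at a true 42%, the threshold.** 0.42 × 70 is about 29 responders and 41 non-responders. The FAS gives 29/70 = 41.4%, lower limit 0.306. Removing 10 failures gives 29/60 = 48.3%, lower limit 0.362. Removing 20 gives 29/50 = 58.0%, lower limit 0.442, which is above 0.42. Over the binomial distribution, with each non-responder removed independently with probability f, the chance that the per-protocol lower limit exceeds 0.42 is 2.6%, 19.9%, 69.8% and 99.0% for f = 0, 25%, 50% and 75%.

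**The 5% trigger.** On 140 patients, 7 exclusions are 5.0% (not met) and 8 are 5.7% (met). If the literal rule applies in all arms and each responds at 60%, there are 0.4 × 140 = 56 non-responders. Removing 25% of them is 14 patients, or 10%.

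**Between arms.** Under a uniform reading, either 3.2.1 for everyone or 8.4 for everyone, the rule-based difference between arms is at most the Week 15 to 18 window. Under a split reading, with rescued patients kept as non-responders and 2.0 g/kg drop-outs treated as missing, equal true rates of 60% and half of the 14 failures removed give 21/28 = 75% for 2.0 g/kg against 42/70 = 60% for 1.0 g/kg. That 15-point gap comes from the exclusion alone.

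**The case against.** The strongest reply is that the SAP already resolves this. Section 3.2.1 applies only where the endpoint cannot be evaluated, and 8.4 gives rescued and discontinued patients a value. Section 7 excludes only major deviators, and these patients are not deviators. Protocol 9.2.1 points the same way, since it counts missed visits as a deviation only when the reason is not clinical. Read together, 3.2.1 would cover only residual gaps, such as a completer whose score was not recorded.

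That reading is reasonable, and it shows that removal of failures is not settled. But it has to be constructed: no text gives 8.4 precedence, 8.2 limits its non-responder rule to the FAS, and 3.2.1 speaks of the same patient being a non-responder in one set and absent from the other. A programmer following 3.2.1 would not be in error.

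A reader might go further and infer three things that the documents do not support.

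- That the PPS will show a false advantage for 2.0 g/kg. This needs the split reading, and 8.4 names discontinued and rescued patients together in one parenthesis.
- That the trial could be declared positive wrongly. The tested proportion is defined on the FAS, where a missing score counts as failure.
- That nearly all failures would be removed. The documents give no share. Beyond the exceptions above, a patient who improves by Week 6 and later returns to the baseline score has not worsened as 8.4 defines it, and could reach Week 24 as an observed non-responder.

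**Conclusion.** The concern holds as an unreconciled conflict: SAP 3.2.1, supported by 8.2 and the evaluability condition in section 7, against 8.4 and the major-deviation condition in section 7. If 3.2.1 is applied literally, the per-protocol rate in the 1.0 g/kg arm rises from 60% to between 67% and 86% for removal shares of 25% to 75%. At the threshold rate of 42%, the per-protocol lower limit exceeds 0.42 in about 20% to 99% of trials over the same range, against 2.6% with no removal. These figures rest on assumed shares and on removal being random among non-responders. The per-protocol robustness check and any per-protocol dose comparisons are at risk; the confirmatory FAS analysis is not. A large difference between arms arises only under the split reading. The point should be fixed before unblinding, but it concerns a supportive analysis.

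**What to change.** In SAP 3.2.1, 7 and 8.2, state that a patient coded as a non-responder under 8.4 because of rescue or rule-driven exit is an evaluable non-responder in both the FAS and the PPS, in all three arms. Limit per-protocol exclusion for a missing Week 24 score to scores missing for other reasons. Apply the same statement to the grip strength, I-RODS and MRC responses, whose definitions in 8.4 already carry the same coding.

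The cost is about two sentences, repeated where needed, before unblinding. Per-protocol response rates will be lower than literal use of 3.2.1 would give. No dose, rescue or exit rule changes.
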